### **The trial involves patients in five ways:**

- 1) Patients assigned to eSym (eSym+) will report their symptoms via the eSym questionnaires delivered through MyChart. Patients are strongly encouraged to report their symptoms at home/between clinic visits with eSym. Study teams and clinicians may elect to ask eSym-eligible patients to complete eSym questionnaires in the clinic via a table, computer, and/or mobile device if patients have difficulties reporting or decline to report at home. Site study teams should consult the central study team before they initiate this workflow.
- 2) A subset of eSym+ patients will be asked to complete a research questionnaire called the “SASS Questionnaire (eSym+ or eSym+ Non-Responder version)” asking about their Self-efficacy, Attainment of information needs, Symptom burden, and Satisfaction with care (see PROMIS, CAHPS, IAM/AIM question banks – Appendices C through G). The eSym+ version is for patients who were assigned to eSym and completed at least one eSym questionnaire. The eSym+ Non-Responder version is for patients who were assigned to eSym but never completed an eSym questionnaire. The questionnaires will stop being administered once a minimum of 1,980 total surveys have been received in accordance with the following breakdown:

SASS Questionnaire accrual numbers							
	Surgery			Medical Oncology			Totals
	eSym+ Version	eSym- Version	eSym+ Non- Responder Version	eSym+ Version	eSym- Version	eSym+ Non- Responder Version	
Site 1	75	75	15	75	75	15	330
Site 2	75	75	15	75	75	15	330
Site 3	75	75	15	75	75	15	330
Site 4	75	75	15	75	75	15	330
Site 5	75	75	15	75	75	15	330
Site 6	75	75	15	75	75	15	330
Totals	450	450	90	450	450	90	1,980

- 3) Select patients NOT assigned to eSym (control group, eSym-) will also be asked to complete the “SASS Questionnaire (eSym- version)” (see Appendices U-X). Both Drug Therapy and Surgical Recover Experience eSym- versions will not ask questions evaluating eSym as the cohort will not be exposed to eSym at the time of the survey. The

questionnaire will stop being administered once a minimum of 1,980 total surveys have been received in accordance with the above breakdown. **\*\* Total number of SASS participants through surveys can be larger or smaller depending on availability.**

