Under a HIPAA waiver, study staff will run reports in Epic as part of the eSyM registry and/or to identify patients meeting eSyM registry criteria to identify medical and surgical patients for eSyM+, eSyM-, eSyM+ Non-Responder SASS questionnaires, and patient qualitative interviews. Select eSyM- patients will be identified and surveyed before eSyM's launch at their site but after the registry has been created, ensuring that they have never been exposed to the program but would have been eligible to use it. Patients eligible to complete the eSyM- questionnaire will be identified using the patient registry and/or a site-developed Epic report to identify patients who had a qualifying surgery or new chemo start within the last 6 months. Patients eligible to complete the eSyM+ and eSyM+ Non-Responder questionnaires will be identified using the registry after eSyM has been launched at their site and 30-60 days after their surgery or new chemotherapy. The eSyM+ SASS questionnaire will be distributed to patients who were assigned to eSyM and completed at least one eSyM questionnaire. The eSyM+ Non- Responder SASS questionnaire will be distributed to patients who were assigned to the eSyM program but never completed an eSyM questionnaire. Sites may begin distributing eSyM+ and eSyM+ Non- Responder questionnaires as soon as they are able to do so after go-live and will continue until a minimum of 75 eSyM+ surveys and a minimum of 15 eSyM+ Non-Responder surveys have been collected for the medical oncology and surgery versions. Patients eligible to participate in the qualitative interviews will be identified using Epic reports and invitations will be sent to patients meeting eSyM program eligibility. Patients may or may not have previously completed SASS or eSyM questionnaires. Interviews will be conducted until thematic saturation is reached, or until 100 interviews have been completed, whichever is reached first.

In addition, under a HIPAA waiver, email and postal addresses will be obtained for all eSyM+, eSyM-, eSyM+ Non-Responder and qualitative interview patients. Email and postal addresses will be utilized to share the SASS questionnaire invitation through REDCap and/or mailing (see Appendix Z) and to send the interview invitations and consent forms via email and/or mailing (see Appendix SS and QQ).

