3.3. Number of Subjects

Considering the 2016 tumor registry-reported analytic case volume at each study site for thoracic, GI and Gyn cancers, 12 patients per month per site for each of surgical and medical oncology is a highly conservative estimate of accrual. With 6 sites, assuming equal cluster size, 432 patients will be enrolled both for each period and for each cohort. Thus, a minimum of 6048 patients are expected to be enrolled to the SW-CRT. (Table 3) We will not have a cap for the number of participants for each site. Thus, the number of participants at the end of the study will be different from site to site.

Table 3: Conservative estimates of the accrual numbers for the SW-CRT

Site	MO/ Surg	Period 1 (Run-in)	Period 2	Period 3	Period 4	Period 5	Period 6	Period 7	Total
BAPT	MO	72	72	72	72	72	72	72	504
	Surg	72	72	72	72	72	72	72	504
MMC	MO	72	72	72	72	72	72	72	504
	Surg	72	72	72	72	72	72	72	504
DFCI	MO	72	72	72	72	72	72	72	504
	Surg	72	72	72	72	72	72	72	504
LCI	MO	72	72	72	72	72	72	72	504
	Surg	72	72	72	72	72	72	72	504
DHMC	MO	72	72	72	72	72	72	72	504
	Surg	72	72	72	72	72	72	72	504
WVU	MO	72	72	72	72	72	72	72	504
	Surg	72	72	72	72	72	72	72	504
Total	MO	432	432	432	432	432	432	432	6048
	Surg	432	432	432	432	432	432	432	

Notes:

- The length of each period is 6 months. The run-in period will be at least 6 months, and it will be adjusted so that the total number of eligible episodes under the control condition can be identical to that under the intervention condition.
- The cells colored by blue or grey indicate the periods where the intervention is rolled out in that hospital.

A subset of eSyM+ patients will be asked to complete a research questionnaire called the “SASS Questionnaire (eSyM+ version)” asking about their Self-efficacy, Attainment of information needs, Symptom burden, and Satisfaction with care.

Table 4: SASS Questionnaire accrual numbers (Survey Cohort)							
Site	Surgery			Medical Oncology			Totals
	eSyM- Version	eSyM+ Version	eSyM+ Non-Responder Version	eSyM- Version	eSyM+ Version	eSyM+ Non-Responder Version	
Site 1	75	75	15	75	75	15	330
Site 2	75	75	15	75	75	15	330
Site 3	75	75	15	75	75	15	330
Site 4	75	75	15	75	75	15	330
Site 5	75	75	15	75	75	15	330
Site 6	75	75	15	75	75	15	330
Totals	450	450	90	450	450	90	1,980

eSyM+ : Intervention condition
eSyM- : Control condition

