The questionnaire will stop being administered once a minimum of 1,980 total surveys have been received in accordance with the above breakdown. (**Table 4**) *** Total number of SASS participants through surveys can be larger or smaller depending on availability.*

A small subset of eSyM- and eSyM+ patients will be invited to take part in a one-time qualitative interview. Patients may or may not have previously completed SASS or eSyM questionnaires. Interviews will continue until thematic saturation is reached, or until 100 interviews are completed, whichever is reached first.

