6.2. Data Analysis

Analysis of Outcomes classified as Type 1:

- For descriptive purposes, we will estimate crude means for continuous outcomes and crude proportions for dichotomous outcomes and calculate corresponding 95% confidence intervals by site. The coefficient of variation is calculated using the site-specific point estimates.
- Next, we estimate the overall mean (or proportion). To this end, a weighted mean and corresponding 95% confidence interval will be calculated using the site-specific point estimates and their standard error estimates, using the inverse of the site-specific variance estimates for the weights.
- In addition, generalized linear models (GLMs) will be used to investigate factors associated with the outcome. In the GLMs, we will account for site variability by treating "site" as a fixed effect. For modeling continuous outcomes, we will use the identity link function. For dichotomous outcomes, the logit link function is used.

Analysis of Outcomes classified as Type 2:

- We will calculate the site-period-specific means (or proportions), adjusted for the factors potentially associated with the outcome. We will calculate the coefficient of variations across sites and also across periods, respectively.
- To this end, we will use generalized linear mixed-effects models (GLMMs). In GLMMs, we will account for site variability by treating "site" as a fixed-effect, secular trend by treating "period" as a fixed-effect, and within-subject variability by treating "subject" as random-effects. For modeling continuous outcomes, we will employ the identity link function. For

dichotomous outcomes, the logit link function will be utilized. G-computation will be used to derive the site-period-specific means (or proportions).

- We will also calculate the site-specific, period-specific, and overall means (or proportions) and corresponding 0.95 confidence interval by taking a weighted average of the site-period-specific mean values (or proportions) obtained through GLMMs. The reciprocal of the variance-covariance matrices of the site-period-specific mean values (or proportions) will be used as the weight.

Analysis of Outcomes classified as Type 3:

- For descriptive purposes, we will estimate crude means for continuous outcomes and proportions for dichotomous outcomes and calculate corresponding 95% confidence intervals by intervention group (eSyM+ vs. eSyM-) and site.

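### The eSyM+ survey sample is recruited in engagement strata with quotas not tied to uptake, and the Type 3 analysis does not reweight them, so the PROMIS and CAHPS differences can be biased by who engaged

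*Protocol*

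**What the plan says.** The Protocol (Section 5.0, Activity 4, paragraph on identifying subjects) defines the post-go-live survey groups by what patients did after exposure: "The eSyM+ SASS questionnaire will be distributed to patients who were assigned to eSyM and completed at least one eSyM questionnaire". Of the other version it says that the "SASS questionnaire will be distributed to patients who were assigned to the eSyM program but never completed an eSyM questionnaire". In each site and cohort, sites keep sending them out "until a minimum of 75 eSyM+ surveys and a minimum of 15 eSyM+ Non-Responder surveys have been collected for the medical oncology and surgery versions".

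Controls are found another way: "Patients eligible to complete the eSyM- questionnaire will be identified using the patient registry and/or a site-developed Epic report". The criterion is a qualifying surgery or new chemotherapy start. Nothing splits controls by likely engagement.

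On stopping, the Protocol says: "The questionnaires will stop being administered once a minimum of 1,980 total surveys have been received in accordance with the following breakdown". The breakdown is 75 eSyM+, 75 eSyM- and 15 Non-Responder surveys per site and cohort. SAP 3.3 repeats it in Table 4 and adds: "Total number of SASS participants through surveys can be larger or smaller depending on availability". The SAP text there opens with "A subset of eSyM+ patients will be asked to complete a research questionnaire" and names only the eSyM+ version, although Table 4 has a separate Non-Responder column.

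For Type 3 outcomes, SAP 6.2 first estimates crude means or proportions "by intervention group (eSyM+ vs. eSyM-) and site". It takes the difference within each site and averages the six differences with inverse-variance weights. Additional GLMs, described as exploring factors related to the outcome, include the intervention indicator, site, age, sex, employment, education, ability to pay bills and confidence with technology. SAP 7.2 applies the same sampling and analysis to CAHPS.

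**The concern.** Selection on engagement operates in one condition only. The mix of engagers and non-engagers among eSyM+ surveys is driven by quotas, while the control mix comes from whoever was invited and answered. If patients who report through a portal differ from those who do not in symptoms, function or satisfaction, the two groups can differ with no eSyM effect at all.

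The SAP treats engagement as non-random elsewhere. For Aim 2a, the primary comparison keeps all exposed episodes whether or not the patient engaged. Engaged patients are compared with pre-go-live controls only after propensity matching on the Table 7 variables. The survey analysis has neither safeguard. It also leaves open whether eSyM+ means both versions or the responder version alone, and these are different comparisons.

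At stake are Aims 2c and 2d, both stated effectiveness aims. A reported PROMIS or CAHPS difference could not be separated from the make-up of the eSyM+ sample.

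**Working it through.** **Inputs from the documents.** Six sites; two cohorts; quotas of 75, 75 and 15 (Protocol Activity 4; SAP Table 4); 0.5 SD as the PROMIS minimally important difference (SAP 6.2).

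**Inputs not in the documents.** Uptake u (share of exposed patients with at least one report) is a study outcome (SAP Table 13). The mean gap D between engagers and non-engagers is not given. Both are shown as ranges.

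**The plan's own figure.** 6 × 2 × (75 + 75 + 15) = 1,980, which matches. No power calculation is given for Aims 2c or 2d.

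**Responder share at the quotas.** 75/90 = 0.833, or 900 of 1,080 eSyM+ surveys.

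**Bias with no true effect.** Assume quotas met exactly and survey response unrelated to engagement, so that the engager share among controls is u. A positive value points toward the engagers' mean.

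- Both versions pooled: (0.833 − u) × D
- Responder version only: (1 − u) × D

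| Uptake | Pooled, D = 0.1 / 0.3 / 0.5 SD | Responder version only, D = 0.1 / 0.3 / 0.5 SD |
|---|---|---|
| 20% | 0.063 / 0.190 / 0.317 | 0.080 / 0.240 / 0.400 |
| 40% | 0.043 / 0.130 / 0.217 | 0.060 / 0.180 / 0.300 |
| 60% | 0.023 / 0.070 / 0.117 | 0.040 / 0.120 / 0.200 |
| 83.3% | 0 / 0 / 0 | 0.017 / 0.050 / 0.083 |
| 90% | −0.007 / −0.020 / −0.033 | 0.010 / 0.030 / 0.050 |

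**Precision of the crude pooled contrast** (unit SD, independent observations, equal sites and cohorts). SE = √[(1/90 + 1/75)/12] = 0.0451, so the 95% half-width is 1.96 × 0.0451 = 0.088 SD. For one cohort, dividing by 6 instead of 12 gives 0.125 SD.

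**Consequence at 40% uptake.** The chance that a nominal 95% interval excludes zero with no effect is 1 − Φ(1.96 − b/SE) + Φ(−1.96 − b/SE), where b is the bias. For D = 0.1 SD, b/SE = 0.96 and the chance is about 16%. For D = 0.3 SD, b/SE = 2.88 and it is about 82%. At 60% uptake the corresponding figures are 8% and 34%.

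**Precision after weighting.** If the weighted responder share is p, the eSyM+ variance per site and cohort is p²/75 + (1 − p)²/15.

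- p = 0.4: 0.00213 + 0.02400 = 0.02613. Half-width = 1.96 × √[(0.02613 + 0.01333)/12] = 0.112 SD.
- p = 0.6: 0.00480 + 0.01067 = 0.01547. Half-width = 1.96 × √[(0.01547 + 0.01333)/12] = 0.096 SD.
- p = 0.2: half-width = 0.135 SD by the same formula.

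**The case against.** **The ratio is not fixed.** A reader might infer that every site ends with exactly 75 to 15. The numbers are minimums, totals may vary, and the Protocol's recruitment text also speaks of inviting all denominator patients. This stands: 0.833 is an assumption about what is collected. But none of these provisions ties the mix to uptake.

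**Controls are not a random sample.** A reader might take them as the natural mix of all eligible patients. The Protocol says that select eSyM- patients are surveyed, and all groups are volunteers for a 20-minute questionnaire. The relevant quantity is the engager share among control respondents. Suppose engagers answer at twice the rate of non-engagers and D = 0.5 SD (both assumed). At 40% uptake, controls are 0.8/1.4 = 57% engagers and the pooled bias is (0.833 − 0.571) × 0.5 = 0.13 SD, not 0.22. At 60% uptake, controls are 1.2/1.6 = 75% engagers and the bias is 0.04 SD. Weighting only the eSyM+ side to registry uptake would then give −0.09 and −0.075 SD, so at 60% uptake it makes matters worse. This stands and shapes the fix.

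**Adjustment is planned.** The GLM includes technology confidence, a plausible proxy for portal use, and may remove part of the bias. It does not alter the crude weighted difference, and it omits several Table 7 engagement variables: race/ethnicity, rurality, insurance, cancer type and comorbidity.

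**The outcomes are secondary.** This stands. Type 3 states no alpha or power, and the all-exposed comparison is written out only for Aim 2a. The crude group means are called descriptive, but the overall difference is built on them.

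**Conclusion.** The plan, followed as written, can give a composition-biased eSyM+ v eSyM- difference for PROMIS and CAHPS. Two conditions are needed: engagement is related to the outcome, and engagers form a different share of eSyM+ surveys than of control respondents. The documents establish neither, so size and direction are unknown. Under the simple assumptions above, the pooled bias at 40% uptake is 0.04 SD for a 0.1 SD gap, inside the 0.088 SD half-width. It is 0.13 or 0.22 SD for gaps of 0.3 or 0.5 SD, outside it. All three are below the 0.5 SD minimally important difference.

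Two stronger readings are not supported. One is that the survey results are certain to favour eSyM: D could take either sign or be near zero, and 0.5 SD is a yardstick for importance, not an estimate of the gap. The other is that the trial's main conclusion is compromised: day-30 EDTR is analysed in all exposed and unexposed patients from medical records and does not use the survey sample. The point should be fixed, but it is confined to Aims 2c and 2d.

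**What to change.** In SAP 6.2 Type 3, and so in 7.2:

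- State that eSyM+ means all exposed patients and includes both survey versions.
- Within each site and cohort, weight responder and non-responder surveys by the inverse of their invitation fractions, that is, eligible patients in the stratum divided by those invited. The weighted eSyM+ sample then has the mix that would have answered without quotas, as the controls do. This assumes that survey response relates to engagement in the same way before and after go-live.
- Use these weights in the site differences and in the GLM, with robust standard errors.
- As a sensitivity analysis, weight eSyM+ to registry uptake and apply a matching non-response adjustment to the controls, for example with the Table 7 variables. Do not weight the eSyM+ side alone.
- Report the two strata separately. Label any responder-only comparison as engaged patients v controls not selected on engagement.

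The cost is SAP text, counts of eligible and invited patients by stratum, and some precision. If the weighted responder share is 40%, the relative weights are 0.4/0.833 = 0.48 and 0.6/0.167 = 3.6, and the half-width rises from 0.088 to about 0.112 SD. At 60% it is 0.096 SD. The loss arises because the small non-responder quota is weighted up.

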**Activity 4 Population:**

- Age  $\geq$  18 years
- Priority population will be patients who meet one of the following:
  - Suspected thoracic cancer AND is undergoing thoracic surgery.
  - Suspected gastrointestinal cancer AND is undergoing gastrointestinal surgery.
  - Suspected gynecologic cancer AND is undergoing gynecologic surgery.
  - Diagnosis of thoracic cancer AND scheduled to start a new treatment plan for thoracic cancer.
  - Diagnosis of gastrointestinal cancer AND scheduled to start a new treatment plan for gastrointestinal cancer.
  - Diagnosis of gynecologic cancer AND scheduled to start a new treatment plan for gynecologic cancer.
- Total population allowed to use eSyM:
  - Any patient at any participating site.

*\*\*Please note – Patients undergoing thoracic, gynecologic, or gastrointestinal surgery may not be diagnosed with cancer. These patients are still eligible for eSyM usage, questionnaire completion, and medical record abstraction.*

**Defining and operationalizing the denominator:**

- To determine if a patient has a diagnosis of one of the priority cancer types, use ICD-10 diagnosis codes: 15.0-16.99 (esophago-gastric) C17.0-C21.9 (small int. colorectal) C22.0-24.9 (hepatobiliary) C23-C25.9 (pancreas), C34-34.9: lung, C53.0-53.9 (cervix) C54-54.9 (uterine) and/or C56-57.9 (ovarian). When it comes time to execute, this list may be modified. CPT and procedure codes as well as EPIC operating room scheduling lists will be used to determine if a patient is scheduled for a priority surgery.
- Participants assigned to eSyM+ may be trained to use eSyM by their local clinic/study staff. Surgical patients may be trained to use eSyM at the time of surgical discharge (or at the site's discretion patients may receive training in how to use eSyM at a preoperative visit). Med Onc patients may be trained to use eSyM at the time of their first chemotherapy dose visit or at the time of a pre-treatment visit for chemotherapy teaching (at the site's discretion). Epic reports may also be used to identify eligible patients who are assigned or will be assigned to eSyM so that training of the eligible patients can be done by study research staff via telephone or email before or after beginning treatment or having surgery.
- Participants in the eSyM- cohort will meet priority population criteria and be seen at a participating site between 1/1/2018 and the site's eSyM go-live date. Participants in the eSyM+ cohort will meet priority population criteria and be seen at a participating site after their eSyM go-live date through March 31, 2024.

**Mode of Participation:** Patients will have a *choice* of their preferred mode of eSyM participation and switching can be accommodated. Patients with a smart phone will be offered that approach first, however all patients will be notified that access to eSyM is available as long as they can access the secure patient portal (MyChart). eSyM can be accessed securely through the MyChart portal on any web-enabled device. Alternatives to smart phone reporting include

participation in eSyM via any web-enabled device (laptop/tablet/desktop). Patients may designate a caregiver willing to elicit their symptoms and report responses on their behalf (proxy reporting). This flexibility facilitates the intervention's reach to frail patients who may be those most likely to benefit. The influence of mode of participation and reliance on self- versus proxy-reporting will be analyzed in multivariable models.

**The denominator is defined above. Automated and/or manual medical record (and/or local cancer registry) review will be done on all patients in the denominator.**

**Number of subjects (per site and overall):** For Activity 4, there will be a *minimum* of 6,048 eSyM+ patient users. Prespecified eSyM- accrual numbers can be found in Appendix TT (SAP). eSyM users and control patients can be from any of the 6 participating sites. We anticipate that each of the 6 hospitals in the stepped wedge trial will have a *minimum* of 900 patients. Protocol does not mandate equal distribution of participants among participating sites. The entire statistical analysis section is predicated on a *minimum* N=6048. Because the goal is broad-based systems-level implementation, we anticipate having much a higher N which will enable us to examine effectiveness in subgroups of interest.

**When, where, and how potential subjects will be recruited:** Once the population definition has been programmed into eSyM/ MyChart, the system will automatically deliver the invitation to use eSyM to the patients in the eSyM+ group (see randomization schedule figure below under the title “stepped wedge rollout”). eSyM- patients will be identified using Epic query reports. Study staff will deliver the invitation to participate in the SASS Questionnaire to all patients in the denominator (eSyM+, eSyM-, and eSyM+ Non- Responder) using the registry before and after eSyM launch until at least 1,980 have participated. Because different patients are reachable by different methods, patients may be contacted through email, postal mail, by phone, or in clinic inviting them to use eSyM and/or participate in the SASS Questionnaire.

There are six versions of the SASS Questionnaire: surgical experience eSyM+, eSyM-, and eSyM+ Non-Responder and drug therapy eSyM+, eSyM-, and eSyM+ Non-Responder. All versions contain validated PRO items (including PROMIS and CAHPs) and validated computer and internet use items from PEW. The eSyM+ versions contain additional items to evaluate usability and satisfaction with eSyM. The eSyM+ Non-Responder versions include additional questions to evaluate why eligible eSyM patients did not respond to the eSyM questionnaires. The SASS Questionnaire may be administered through REDCap, by phone, email, postal mail, or in clinic. Multiple methods of collection are allowed in order to minimize barriers to participation. As needed, patients will also be offered eSyM training through in-person, phone, and/or virtual visits.

The patient qualitative interviews will follow the interview guide in Appendix RR. The interview will ask questions regarding patients' overall experience with the program, suggested improvements they would make to the eSyM symptom questionnaire or the overall program, and any potential or real barriers to accessing or using the program. The interviews may take place by phone, via Zoom/video conference, or in-person. Multiple methods of collection are allowed to minimize barriers to participation.

**Materials that will be used to recruit subjects:** See Appendices M and N for the message that will be sent to patients inviting them to participate in the questionnaire and/or eSyM, respectively. As a reminder, participating in the SASS questionnaire or eSyM survey will not influence a patient's medical care in any manner. The purpose of these questionnaires is to help care teams learn about the best way to help patients cope with symptoms between visits (for medical oncology) and after surgery (for surgical patients).

See Appendices SS and QQ for the message and consent form that will be sent to patients inviting them to participate in the qualitative interview. Participating in the qualitative interview will not influence a patient's medical care in any manner. The purpose of these interviews is to gather direct patient feedback for study research staff about eSyM to inform future optimizations to the program.

